7.3 Baseline Disease Evaluation

For the pharmacokinetic analysis set, the subject population set of the pharmacokinetic analysis set for which at least one primary endpoint was obtained, and safety analysis set, each variable at baseline will be calculated.

Table 7.3-1 Baseline Pathologic Evaluation		
Variable	Method	Level
Cardiothoracic ratio (%)	Descriptive statistics	-
NYHA classification	Distribution	Class I, Class II, Class III, Class IV

Table 7.3-1 Baseline Pathologic Evaluation		
Variable	Method	Level
Severity of lower limb edema	Distribution	None, Mild, Moderate, Severe
Pulmonary congestion	Distribution	None, Mild, Moderate, Severe
Presence of jugular venous distension	Distribution	Yes, No
Jugular venous distension (cm)	Descriptive statistics	-
Presence of hepatomegaly	Distribution	Yes, No
Hepatomegaly (cm)	Descriptive statistics	-
Pulmonary rales	Distribution	Yes, No
Third cardiac sound	Distribution	Yes, No
Daily urine volume	Distribution	< 1500 mL, ≥ 1500 mL
Creatinine	Distribution	< 2 mg/dL, ≥ 2 mg/dL
Plasma AVP concentration	Distribution	≤ 3.1 pg/mL, > 3.1 pg/mL
Albumin	Distribution	< 3 g/dL, ≥ 3 g/dL

7.4 Treatment Compliance

This will be summarized for the pharmacokinetic analysis set, subject population set of the pharmacokinetic analysis set for which at least one primary endpoint was obtained, and safety analysis set. Distributions for presence or absence of discontinuation during IMP (injection) administration will be calculated. Distributions for presence or absence of days of incomplete IMP (injection) administration as well as days of missing an IMP (tablet) dose will also be calculated.

7.5 Prior and Concomitant Medications

For the pharmacokinetic analysis set, subject population of the pharmacokinetic analysis set for which at least one primary endpoint was obtained, and safety analysis set, distributions for usage of concomitant medication on the initial IMP administration day will be calculated.

Table 7.5-1 Usage of Concomitant Medication on Initial IMP Administration Day	
Variable	Level
Use of loop diuretic	Monotherapy with loop diuretic Loop diuretic + other diuretic
Dose of loop diuretic (Furosemide equivalent ^a)	< 40 mg/day, ≥ 40 mg/day and < 80 mg/day, ≥ 80 mg/day
Category of diuretic *Concomitant use of diuretic drugs other than loop diuretic, thiazide diuretic, and anti-aldosterone drug is not summarized.	Monotherapy with loop diuretic, Loop diuretic + thiazide diuretic, Loop diuretic + anti-aldosterone drug, Loop diuretic + thiazide diuretic + anti-aldosterone drug
Thiazide diuretic	Yes, No
Anti-aldosterone drug	Yes, No
Drugs for heart failure other than diuretics	Yes, No
Digitalis product	Yes, No
ACE inhibitor	Yes, No
Beta blocker	Yes, No
Angiotensin receptor blocker	Yes, No

^aFurosemide equivalent dose of 40 mg is defined as bumetanide, 1 mg; piretanide, 6 mg; azosemide, 60 mg; and torasemide, 8 mg.

7.6 Protocol Deviations

For randomized subjects, distributions for presence or absence of deviations in each CRF classification (Dosing, Inclusion/Exclusion Criteria, Met Withdrawal Criteria But Was Not Withdrawn, Prohibited Concomitant Medications) will be calculated. Distributions of subjects with at least one deviation will also be calculated.

8 Efficacy Analysis

The following analyses will be performed in the efficacy analysis set. Each analysis will be exploratory, and multiplicity of testing is not considered.

8.1 Body Weight

Analysis of covariance using baseline weight as covariate will be performed on the change from baseline in body weight after final administration to calculate the least-square mean of the difference between each OPC-61815 injection group and tolvaptan 15-mg tablet group and its two-sided 95% confidence interval (based on the t

distribution). At each time point, descriptive statistics of measurement and change and percent change from baseline will be calculated for each group.

For changes in body weight from baseline, a timecourse (mean \pm standard deviation) from Day 1 of treatment period to follow-up will be created for each treatment group. For changes in body weight from baseline to the final IMP administration, a bar graph of least square means (two-sided 95% confidence interval) with the horizontal axis representing treatment groups will be created.

8.2 Congestive symptoms

8.2.1 Lower limb Edema, Other Edema, and Pulmonary Congestion (Chest X-ray)

The proportion of responders (subjects who have congestive symptoms at baseline and have a “markedly improved” or “improved” response evaluated with reference to [Table 8.2-1](#)) and the proportion of subjects who achieve resolution (subjects who have congestive symptoms at baseline and in whom the symptoms resolve after IMP administration) of lower limb edema and pulmonary congestion after final administration are calculated for each OPC-61815 injection group, together with the difference in the proportions between each OPC-61815 injection group and tolvaptan 15-mg group with the two-sided 95% confidence intervals (exact) of each difference.

Changes in the severity of each congestive symptom at each time point (from baseline to after each administration and to after final administration) will be summarized for each group in a shift table.

For other edema, analysis will not be performed.

Table 8.2-1 Response of Lower limb Edema, Other Edema, and Pulmonary Congestion		
	Response	Description
1	Markedly improved	Resolution of symptom or improvement by 2 grades or more
2	Improved	Improvement by 1 grade (if the symptom has resolved, an assessment of “markedly improved” is given instead)
3	No change	No change in symptom, or absence of symptom throughout the trial
4	Worsened	Worsening by 1 grade or more

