3.7.2 Prior and Concomitant Medication

The investigator or subinvestigator will document in the CRF all the drugs and therapies given to the subject between the day of signing informed consent and end-of-trial/withdrawal examination. The investigator or subinvestigator will also document in

the CRF the drugs and therapies given for the treatment of AEs by the last scheduled contact or the drugs/therapies that caused AEs.

3.7.3 **Efficacy Assessments**

3.7.3.1 **Body Weight**

The investigator or subinvestigator will have the subject void his/her bladder at least once after awakening and subsequently weigh the subject on an appropriately calibrated scale before breakfast after taking precautions to minimize the effect of defecation and clothing. The date and time of measurement and the weight (read to 1 decimal place in kilograms) will be recorded in the source documents and CRF. If the scale used measures to 2 or more decimal places, the reading is rounded to 1 decimal place and recorded.

3.7.3.2 Congestive Symptoms (Lower Limb Edema, Other Edema, Jugular Venous Distension, Pulmonary Rales, Third Cardiac Sound, and Hepatomegaly)

The investigator or subinvestigator will examine the subject for congestive symptoms (lower limb edema, other edema, jugular venous distension, hepatomegaly, pulmonary rales, and third cardiac sound) and decides whether the subject has the symptoms and assesses the severity of each symptom in the manner described below. The investigator or subinvestigator will document the date of assessment together with the results of assessment in the source documents and CRF.

(1) Lower Limb Edema

The severity of edema in the subject's tibial border or dorsum of the foot will be assessed in the sitting position using the scale below.

Table 3.7.3.2-1		Scale for Lower Limb Edema		
	Severity	Description		
0	Absent	No indentation		
1	Mild	Slight indentation		
2	Moderate	Deep indentation		
3	Severe	Visible edema		

(2) Other Edema

The same scale to be used in assessment of lower limb edema will be used. The same area will be used for assessment both before and after IMP administration. The area of assessment will be recorded in the source documents and CRF.

(3) Jugular Venous Distension

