7.4.2 Congestive Symptoms

7.4.2.1 Lower Limb Edema, Other Edema, and Pulmonary Congestion (Chest X-ray Finding)

The proportion of responders (subjects with a "markedly improved" or "improved" response is evaluated with reference to Table 7.4.2.1-1) and the proportion of subjects who achieve resolution [subjects who have congestive symptoms at baseline (immediately before first IMP administration) and in whom the symptoms resolve after IMP administration] of lower limb edema, other edema, and pulmonary congestion after final administration are calculated for each OPC-61815 injection group, together with the difference in the proportions between each OPC-61815 injection group and tolvaptan 15-mg group with the 95% confidence interval of each difference.

Changes in the severity of each congestive symptom at each time point (from baseline to after each administration and to after final administration) will be summarized for each group in a shift table.

		Response of Lower Limb Edema, Other Edema, and Pulmonary Congestion
	Response	Description
1	Markedly improved	Resolution of symptom or improvement by 2 grades or more
2	Improved	Improvement by 1 grade (if the symptom has resolved, an assessment of "markedly improved" is given instead)
3	No change	No change in symptom, or absence of symptom throughout the trial
4	Worsened	Worsening by 1 grade or more

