8.2.2 Jugular Venous Distension, Hepatomegaly, and Cardiotoracic Ratio

Change from baseline in jugular venous distension and cardiotoracic ratio after final administration will be analyzed using analysis of covariance with baseline value as

covariate to calculate the least square mean of the difference between each OPC-61815 injection group and tolvaptan 15-mg tablet group and its two-sided 95% confidence intervals (based on the t distribution). Descriptive statistics of the measurements and their changes from baseline at each time point for jugular venous distension, hepatomegaly, and cardiothoracic ratio will be calculated for each group.

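### Lower limb edema and pulmonary congestion are graded 0–3, but SAP 8.2.1 compares the arms only on two yes/no cuts; adding a full-scale comparison would usually be more precise and costs little

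*SAP*

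**What the plan says.** Protocol 3.7.3.2 grades lower limb edema from 0 (absent) to 3 (severe): "The severity of edema in the subject's tibial border or dorsum of the foot will be assessed in the sitting position using the scale below". Protocol 3.7.3.3 grades pulmonary congestion on chest X-ray over the same range.

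SAP 8.2.1 turns the change in grade into four ordered responses. The top one is defined as "Resolution of symptom or improvement by 2 grades or more". Two proportions are then formed:

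- **Responder:** "subjects who have congestive symptoms at baseline and have a" response in one of the top two categories, that is, any improvement of at least one grade.
- **Resolution:** "subjects who have congestive symptoms at baseline and in whom the symptoms resolve after IMP administration".

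Both are reported for every dose, "together with the difference in the proportions between each OPC-61815 injection group and tolvaptan 15-mg group with the two-sided 95% confidence intervals (exact) of each" contrast with the tablet. The exact method is not named. Protocol 7.4.2.1 specifies the same two differences. The grades also appear in shift tables, but by group and without a contrast to the tablet.

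SAP 8.2.2 treats jugular venous distension and cardiothoracic ratio differently. It analyses change by ANCOVA with the baseline value as "covariate to calculate the least square mean of the difference between each OPC-61815 injection group and tolvaptan 15-mg tablet group" and a t-based interval. SAP 8.1 does the same for body weight. The opening of SAP section 8 declares all efficacy analyses exploratory.

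**The concern.** Each cut discards part of what was recorded. The responder cut scores a fall from 3 to 0 the same as a fall from 3 to 2, and a worsening the same as no change. The resolution cut gives no credit for a fall from 3 to 1, which the SAP's own response table puts in its best category. Whether resolution is reachable depends strongly on baseline grade, which is not adjusted for.

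The secondary objective includes comparing efficacy with the tablet. Group size was set for Day 1 tolvaptan exposure, and entry requires only one of three signs, so the number of subjects with any given sign may be below 10 per arm. With so few subjects, leaving the grade and its baseline out of the only between-arm comparison gives up precision that the trial has already paid for.

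**Working it through.** **Inputs from the documents.** Completers: 50/5 = 10 per arm. Starters: 55/5 = 11 per arm. Two-sided 95% exact intervals. Grades 0–3. No power, response rate, grade mix, effect or SD is stated for these signs, so there is no planned figure to reproduce.

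**How wide the planned intervals are.** With 9/10 against 5/10 responders, the pooled proportion is 0.70 and z = 0.40/√(0.70 × 0.30 × 2/10) = 0.40/0.205 = 1.95. That is just short of 1.96, so a 40-point observed difference does not exclude zero. With 5/10 against 5/10, a score-based exact interval runs to about ±40–45 points, depending on how it is constructed.

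**Assumed model.** Final grade = baseline grade minus a normal improvement with mean μ and SD σ, rounded and clipped to 0–3. Then:

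- P(responder) = Φ((μ − 0.5)/σ), whatever the baseline grade.
- P(resolution from grade b) = Φ((μ − b + 0.5)/σ).

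**Example.** σ = 0.6, tablet μ = 0.5, injection μ = 1.3 (a 0.8-grade difference), baseline grades 1/2/3 in 34/40/26%.

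- Responder: Φ(0) = 50% against Φ(1.33) = 91%.
- Resolution, tablet: 0.34 × 0.50 + 0.40 × 0.048 + 0.26 × 0.0004 = 19%.
- Resolution, injection: 0.34 × 0.909 + 0.40 × 0.369 + 0.26 × 0.023 = 46%.

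At 10 per arm the expected z is 0.409/√(0.705 × 0.295 × 0.2) = 2.0 for responder and 0.274/√(0.326 × 0.674 × 0.2) = 1.3 for resolution. The resolution cut is weak because subjects starting at grade 2 or 3 seldom reach 0.

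**Simulation.** 10 per arm, σ = 0.6, difference 0.8 grade, score-based exact comparison, 6,000 trials per row. Entries are the percentage of trials in which the 95% comparison excludes zero. Gains are taken before rounding.

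| Baseline mix 1/2/3 (%) | Tablet μ | Responder | Resolution | Adjusted grade change | Gain over responder | Gain over resolution |
|---|---|---|---|---|---|---|
| 60/30/10 | 0.3 | 57 | 33 | 63 | 6 | 29 |
| 60/30/10 | 0.5 | 50 | 32 | 59 | 9 | 27 |
| 60/30/10 | 0.7 | 37 | 28 | 51 | 15 | 23 |
| 34/40/26 | 0.3 | 59 | 21 | 66 | 7 | 45 |
| 34/40/26 | 0.5 | 50 | 22 | 64 | 13 | 42 |
| 34/40/26 | 0.7 | 37 | 23 | 60 | 23 | 38 |
| 20/40/40 | 0.3 | 59 | 14 | 67 | 8 | 53 |
| 20/40/40 | 0.5 | 49 | 17 | 66 | 17 | 49 |
| 20/40/40 | 0.7 | 37 | 20 | 64 | 28 | 44 |

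For tablet μ of 0.5 or 0.7 the gains are roughly 10–27 points (responder) and 25–48 points (resolution). At μ = 0.3 the responder gain is 6–8 points. With no true difference, ANCOVA excluded zero in 4–6% of trials and Mann-Whitney in 3–7%.

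**Where the gain shrinks.** 10 per arm, σ = 0.6, tablet μ = 0.5:

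- Difference 0.4 grade: responder 19% against ANCOVA 24% (middle mix); 17% against 19% (80/20/0 mix).
- Difference 0.8 with a 90/10/0 mix: 48% against 52%.
- Difference 0.8 with every sign mild: 51% against 52%. The two cuts then coincide.

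**Effect of the unnamed exact method.** With a 40/40/20 mix, a 0.75-grade difference and σ = 0.7, ANCOVA has 48%. The responder cut has 39% with a score-based exact method and 22% with Fisher; resolution has 19% and 9%. So part of the loss can come from the interval method and not from the cut.

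**What the full-scale interval looks like.** At 10 per arm the ANCOVA interval is about 0.7–1.2 grades wide at σ = 0.6, and about 1.3–1.5 at σ = 0.9 with mixed grades.

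**The case against.** The strongest reply is that this is an exploratory estimate with a confidence interval. No test or margin depends on it, so precision is the right yardstick and power only illustrates it. That stands.

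The efficacy comparison also does not rest on these two signs. Body weight, jugular venous distension and cardiothoracic ratio already have baseline-adjusted comparisons with the tablet. The two proportions are protocol-specified and easy to read. Jugular distension and cardiothoracic ratio are continuous, so borrowing their model for a four-level grade with a floor at 0 assumes equal spacing between grades. All of this stands too, and it is why the addition should sit beside the planned rates and include a rank-based estimate.

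Sample size is the larger limit, and no analysis choice cures it: even full-scale power at a 0.4-grade difference is at most about 24%.

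A reader might infer that the plan throws the grades away. It does not, because the shift tables keep them descriptively; what is missing is a comparison between arms. A reader might also infer that the responder and resolution differences should be demoted. The documents give no ground for that.

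**Conclusion.** The point holds as a cheap improvement. SAP 8.2.1 compares the arms on these signs only through two dichotomies, without adjustment for baseline grade, in at most about 10–11 subjects per arm. A full-scale comparison would usually be more precise: in nearly all settings it equalled or beat both cuts to within simulation error.

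A reader might infer that the plan carries a fixed, known loss of power. The documents do not support that, since every figure depends on assumed inputs. With mixed baseline grades, a 0.8-grade difference, SD 0.6, a score-based exact method and 10 per arm, the gain is roughly 10–27 points over responder and 25–48 over resolution; over all nine tabulated settings it spans 6–28 and 23–53. It falls to about 0–5 points over responder when nearly all signs are mild or the difference is 0.4 grade. Other grade mixes, effects or exact methods would move these figures in either direction.

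**What to change.** Keep the responder and resolution differences with their confidence intervals. Add to SAP 8.2.1, for lower limb edema and for pulmonary congestion, in subjects with the sign at baseline and for each dose against the tablet after final administration:

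1. the Mann-Whitney probability of a better grade change, with its 95% CI, which does not assume equal spacing of grades;
2. the mean difference in grade change adjusted for baseline grade, using the SAP 8.2.2 model, with a two-sided 95% CI.

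Record the addition in SAP section 14. Naming the exact method for the proportions would also help a reader interpret those intervals.

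The cost is a short SAP insertion and a few extra exploratory tables, with no new data or subjects. The adjusted mean difference is less directly readable than a rate and assumes equal grade spacing; the retained rates and the rank-based estimate cover that. Both new estimates will still be imprecise.

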8.2.2 Jugular Venous Distension, Hepatomegaly, and Cardiotoracic Ratio

Change from baseline in jugular venous distension and cardiotoracic ratio after final administration will be analyzed using analysis of covariance with baseline value as

covariate to calculate the least square mean of the difference between each OPC-61815 injection group and tolvaptan 15-mg tablet group and its two-sided 95% confidence intervals (based on the t distribution). Descriptive statistics of the measurements and their changes from baseline at each time point for jugular venous distension, hepatomegaly, and cardiothoracic ratio will be calculated for each group.

8.2.3 Pulmonary Rales and Third Cardiac Sound

The proportion of subjects who achieve resolution of pulmonary rales and third cardiac sound (subjects who have the sign at baseline and who do not have the sign after IMP administration) will be calculated in each OPC-61815 injection group together with the difference in the proportion between each OPC-61815 injection group and tolvaptan 15-mg group and its two-sided 95% confidence intervals (exact).

Changes in the severity of pulmonary rales and third cardiac sign at each time point (from baseline to after each IMP administration and to after final administration) will be summarized for each group in a shift table.

8.2.4 NYHA Classification

Changes in NYHA classification at each time point (from baseline to after each administration and to after final administration) will be summarized for each group in a shift table.

8.3 Subgroup Analyses

Subgroup Analyses will not be performed in this trial.

9 Safety Analyses

The following analyses will be performed for each group (including the entire OPC-61815 group) in the safety analysis set.

9.1 Extent of Exposure

Distributions of the number of subjects on each number of administration days will be calculated. Descriptive statistics of the number of administration days will be calculated.

9.2 Adverse Events

All adverse events (AEs) will be coded by system organ class (SOC) and preferred term (PT) (Medical Dictionary for Regulatory Activities [MedDRA]). The incidence of the following events will be summarized for all events, by SOC, and by PT.

- Treatment-emergent AEs (TEAEs)

- TEAEs by severity
- TEAEs with an outcome of death
- Serious TEAEs
- TEAEs leading to discontinuation of the IMP

If there are multiple occurrences of the same event in the same period in the same subject, the event with the highest severity will be selected. The above summaries will also be prepared for TEAEs potentially causally related to the IMP.

For TEAEs, a summary table will also be created for any TEAE that occurs in more than 2 subjects in any group.

9.3 Clinical Laboratory Data

For hematology, serum chemistry (excluding PAP and TRACP-5b), and urinalysis in the protocol “Table 3.7.4.2-1 Clinical Laboratory Assessments” (at the central laboratory), the following will be summarized.

Descriptive statistics of clinical laboratory values (excluding qualitative urinalysis other than pH) as well as of the changes from baseline in values at each time point and after final administration will be calculated. The results of qualitative urinalysis at each postdose time point and after final administration compared with baseline results will be summarized in a shift table. Each clinical laboratory value excluding qualitative urinalysis will be categorized into “within reference range,” “below the lower limit of reference range,” or “above the upper limit of reference range” using the institutional standard values to generate a shift table summarizing laboratory data at each postdose time point and after final administration compared with baseline.

For parameters excluding qualitative urinalysis, a scatter diagram of values after the final administration with comparison to baseline will be created in each group.

For presence or absence of an elevation in AST or ALT that is ≥ 3 times the upper limit of normal of the institutional standard values as well as an elevation in total bilirubin ≥ 2 times the upper limit of normal of the institutional standard values at any point after IMP administration, the number and percentage of subjects will be calculated.

9.4 Vital Sign Data

Descriptive statistics will be calculated for vital signs together with the changes from baseline at each time point and after final administration.

9.5 **Electrocardiogram Data**

Descriptive statistics of each 12-lead electrocardiogram (ECG) parameter and the changes from baseline in each parameter at each time point and after final administration will be calculated.

The number and percentage of subjects who have a QTc interval (QTcB, QTcF) of “> 450 msec”, “> 480 msec”, and “> 500 msec” at at least one postdose time point or after final administration will be calculated. In addition, the number and percentage of subjects who show a change of “> 30 msec” and “> 60 msec” in QTc interval from baseline at at least one postdose time point or after final administration will be calculated. The numbers and percentages of subjects will also be calculated at baseline and each postdose time point in the same manner. “Normal” and “abnormal” assessments at each postdose time point and after final administration compared with baseline will be summarized in a shift table. “Normal” and “abnormal” assessments by the trial site (investigator or subinvestigator) will be used instead of the assessments by the central ECG analysis laboratory.

10 **Pharmacokinetic Analyses**

This section describes the pharmacokinetics of primary and secondary endpoints.

- 1) Endpoints
 - a) Primary Endpoint :
 - C_{max} and AUC_{24h} of plasma tolvaptan on Day 1 of treatment period
 - b) Secondary Endpoints:
 - i) Plasma concentrations of OPC-61815, tolvaptan, DM-4103 and DM-4107
 - ii) Plasma pharmacokinetic parameters of OPC-61815, tolvaptan, DM-4103 and DM-4107
 - Day 1 of treatment period: C_{max}^a , AUC_{24h}^a , AUC_t , AUC_{∞} , t_{max} , λ_z , $AUC_ \%Extrap$, t_{last} , $t_{1/2,z}$, CL^b , CL/BW^b , V_z^b , V_z/BW^b , CL/F^c , $CL/F/BW^c$
 - Day 1, Day 2, Day 3, Day 4, and Day 5 of treatment period: C_{24h}^d
 - Day 5 of treatment period: $R_{5,ac}(C_{24h})$

^aExcluding tolvaptan

^bCalculated only for OPC-61815 after administration of OPC-61815 injection

^cCalculated only for tolvaptan after administration of tolvaptan 15-mg tablet

^dFor calculation of descriptive statistics, C_{24h} will be handled as plasma concentrations.

iii) Ratio of the AUC of metabolite to that of OPC-61815^e

Day 1 of treatment period: AUC_{∞} , AUC_{24h} , and AUC_t

^eCalculated only for the OPC-61815 injection groups

2) Handling of Data

a) Acceptance or nonacceptance of data will be determined in accordance with Section 3.4 Exclusion From Pharmacokinetic Analysis of the Manual Standard Practice for Noncompartmental Pharmacokinetic Analysis (Version 1.0). In other words, in this trial, data matched to the following conditions will not be used.

- To calculate actual time postdose, the actual start date and time of administration of the active drug (start time of administration for oral tablets and injections may be different).
- For each analyte, if blood sampling is conducted outside the time window for the analyses below, the data will be excluded from the calculation of descriptive statistics for plasma concentrations at that time point. However, it will be used for the calculation of pharmacokinetic parameters, and if the calculation is determined to be unsuitable, the parameter will not be adopted.

Table 10-1 Acceptable Window for Analysis of OPC-61815

Plasma Concentration Sampling Time Point		Acceptable Window
Day 1	Before start of IMP administration	From 2 hours to immediately before start of IMP administration
	1 hour after start of IMP administration	Within 5 minutes after end of IMP administration ^a
	1.5 hours after start of IMP administration	Specified time point \pm 5 minutes
	2 hours after start of IMP administration	Specified time point \pm 5 minutes
	4 hours after start of IMP administration	Specified time point \pm 20 minutes
	6 hours after start of IMP administration	Specified time point \pm 30 minutes
	12 hours after start of IMP administration	Specified time point \pm 1 hour
Day 2	24 hours after start of IMP administration on Day 1 (and before administration on Day 2)	22 to 24 hours after start of administration on Day 1
Day 3	24 hours after start of IMP administration on Day 2 (and before administration on Day 3)	22 to 24 hours after start of administration on Day 2
Day 4	24 hours after start of IMP administration on Day 3 (and before administration on Day 4)	22 to 24 hours after start of administration on Day 3
Day 5	24 hours after start of IMP administration on Day 4 (and before administration on Day 5)	22 to 24 hours after start of administration on Day 4
Day 6	24 hours after start of IMP administration on Day 5	22 to 24 hours after start of administration on Day 5

^aFor the tolvaptan 15-mg tablet group, within 1 hour \pm 5 minutes after start of IMP administration (= after end of IMP administration)

Table 10-2 Acceptable Window for Analysis of Analytes other than OPC-61815

Plasma Concentration Sampling Time Point		Acceptable Window
Day 1	Before start of IMP administration	From 2 hours to immediately before start of IMP administration
	1 hour after start of IMP administration	Within 6 minutes after end of IMP administration ^a
	1.5 hours after start of IMP administration	Specified time point \pm 10 minutes
	2 hours after start of IMP administration	Specified time point \pm 10 minutes
	4 hours after start of IMP administration	Specified time point \pm 35 minutes
	6 hours after start of IMP administration	Specified time point \pm 40 minutes
	12 hours after start of IMP administration	Specified time point \pm 1 hour
Day 2	24 hours after start of IMP administration on Day 1 (and before administration on Day 2)	22 to 24 hours after start of IMP administration on Day 1
Day 3	24 hours after start of IMP administration on Day 2 (and before administration on Day 3)	22 to 24 hours after start of IMP administration on Day 2
Day 4	24 hours after start of IMP administration on Day 3 (and before administration on Day 4)	22 to 24 hours after start of IMP administration on Day 3
Day 5	24 hours after start of IMP administration on Day 4 (and before administration on Day 5)	22 to 24 hours after start of IMP administration on Day 4
Day 6	24 hours after start of IMP administration on Day 5	22 to 24 hours after start of IMP administration on Day 5

^aFor the tolvaptan 15-mg tablet group, within 1 hour \pm 6 minutes after start of IMP administration
(= after end of IMP administration)

- If a subject in the tolvaptan 15-mg tablet group experiences vomiting within 8 hours (twice the median t_{max} [4 hours¹]) after IMP administration, none of the postdose plasma concentration data on that day will be used for the calculation of descriptive statistics. Of the parameters calculated with data including plasma concentrations excluded from descriptive statistics, the parameters determined to be unsuitable for the calculations will not be adopted.
- None of the plasma concentrations after use of drugs or food (see Protocol Version 2 Table 4.1-3) which may inhibit or induce CYP3A4 activity will be used (This also applies to plasma concentrations of the following day or later). Of the parameters calculated with data including plasma concentrations excluded from descriptive statistics, the parameters determined to be unsuitable for the calculations will not be adopted.
- If the administration method specified in the protocol (see below) is not applied to administer the IMP, the instructions listed below will be followed.
 - a) Tolvaptan 15-mg tablet group: One tablet is taken with water once daily.
 - For the tolvaptan 15-mg tablet group, in the event of overdosing or missing a dose, plasma concentration at predose on that day will be used, but none of the plasma concentrations after that time point (including the plasma concentrations after administration on the following day or later) will be used for the calculation of descriptive statistics.

b) OPC-61815 injection 2 mg, 4 mg, 8 mg, and 16 mg groups: The assigned dose is administered intravenously for 1 hour (acceptable range: 55 to 65 minutes) once daily.

- For OPC-61815 injection 2 mg, 4 mg, 8 mg, and 16 mg groups, in the event of insufficient dose administration, overdosing, or missing a dose, plasma concentration at predose on that day will be used, but the plasma concentrations after that time point (including the plasma concentrations after administration on the following day or later) will not be used for the calculation of descriptive statistics. In the event of full dose administration but outside the acceptable window because of interruption, etc or full dose administration with an unknown administration time, plasma concentrations after administration on that day will not be used (plasma concentrations at predose on the following day and after administration on the following day or later will be used).

Of the parameters calculated with data including plasma concentrations excluded from descriptive statistics, the parameters determined to be unsuitable for the calculations will not be adopted.

- For each analyte, if a quantitative value is obtained at predose on Day 1, and the value exceeds 5 % or more of the highest value of the period between 1 hour and 24 hours after administration on Day 1, the plasma concentrations for that analyte at predose and thereafter will be excluded from the calculation of descriptive statistics. Parameters of the analyte with all of the plasma concentrations excluded from the calculation of descriptive statistics will not be adopted.
- b) Plasma concentrations below lower limit of quantitation that occur prior to and after the first measurable concentration will be imputed to 0 (ng/mL) and missing. Lower limit of quantitation of each analyte is listed in [Appendix 3](#).
- c) Concentrations reported as Not Analyzed (NA) or Not Determined (ND) are regarded as missing values.

3) Statistical Analysis Method

- a) Primary Endpoint
 - i) For primary endpoint, analysis will be performed for the subject population set of the pharmacokinetic analysis set for which at least one primary endpoint was obtained.
 - ii) For “[1a\)](#) Primary Endpoint,” descriptive statistics will be calculated for each parameter by treatment group.
 - iii) For “[1a\)](#) Primary Endpoint,” logarithm converted value (natural logarithm) will be used to calculate the mean difference (each OPC-61815 injection group – tolvaptan 15-mg tablet group) and the 95% confidence interval of the difference.
- b) Secondary Endpoints
 - i) For secondary endpoints, analyses will be conducted for the pharmacokinetic analysis set.

- ii) For “1)b) Secondary Endpoints i),” descriptive statistics at each blood sampling point will be calculated by administration date, analyte, and treatment group.
- iii) For “1)b) Secondary Endpoints ii)” (excluding λ_z , λ_z (lower), λ_z (upper), λ_z (point) and λ_z (Rsq)), descriptive statistics of each parameter will be calculated by administration date, analyte, and treatment group.
- iv) For “1)b) Secondary Endpoints iii),” descriptive statistics of each parameter will be calculated by analyte and treatment group.

c) Descriptive Statistics

Descriptive statistics to be calculated for plasma drug concentration will be number of analyzed subjects, number of subjects for which concentrations data were obtained (excluding missing data or unadopted data), arithmetic mean, standard deviation, coefficient of variation, minimum, median, and maximum. However, descriptive statistics will be calculated only at the time point when the number of subjects for which data were obtained (excluding missing data or unadopted data) exceeds half of the number of analyzed subjects in each group.

For variables other than plasma drug concentration, descriptive statistics to be calculated will be number of analyzed subjects, number of subjects for which data were obtained (excluding incalculable data or unadopted data), arithmetic mean, standard deviation, coefficient of variation, geometric mean, minimum, median, and maximum. However, descriptive statistics will be calculated only when the number of subjects for which data were obtained (excluding Not Determined (ND) or unadopted data) exceeds half of the number of analyzed subjects in each group.

11 Pharmacodynamic Analyses

Analyses will be performed in the pharmacodynamic analysis set.

For each of the endpoints listed below, descriptive statistics (number of subjects, mean, standard deviation, minimum, median, and maximum) of the measurement and the change from baseline will be calculated for each group at each time point. For daily urine volume, daily fluid intake, and daily fluid balance after IMP administration on Day 1 and after IMP administration on Day 5, the difference (each OPC-61815 injection group – tolvaptan 15-mg tablet) in mean change from baseline and its 95% confidence interval (based on t distribution) will be calculated.

For daily urine output, a transition chart of measurements (mean \pm standard deviation) from the run-in period to Day 5 will be created in each group. For changes from baseline after IMP administration on Day 1 and after IMP administration on Day 5, a bar graph of

the mean (two-sided 95% confidence interval) with the horizontal axis representing treatment groups will also be created.

- Serum sodium concentration, serum potassium concentration (at the central laboratory)
- Serum osmolality
- Biomarkers (plasma AVP concentration, plasma BNP concentration, plasma renin activity, serum NT-proBNP, serum troponin concentration)
- Daily urine volume
- Daily fluid intake
- Daily fluid balance
- Daily urine sodium excretion
- Daily urine potassium excretion
- Urine osmolality

12 Pharmacogenomic Analyses

No pharmacogenomic analysis will be performed in this trial.

13 Interim Analysis

No interim analysis will be performed in this trial.

14 Changes in the Planned Analyses

- For further clarification, handling of discontinued subjects and subjects with missing data was added to Protocol 6.1.1. Pharmacokinetic Analysis Set.
- For erroneous entry, “V” described in Protocol 6.1.2 (1) (b) Secondary endpoints 2 was changed to “V_z.” Since “V_z/BW” was erroneously omitted, it was added.
- For omission in entry, an explanatory note on treating C_{24h} as the plasma concentration for the calculation of descriptive statistics was added.
- For omission in entry, a note considering IMP administration methods in addition to the manual on data handling was added.
- In Protocol 6.1.2 (3) Analytical Method 2), the analysis set for primary endpoints was added for clarification.
- In Protocol 6.1.2 (3) Analytical Method 2), the calculation method in “6.1.2 (1) (b) Secondary endpoints 3)” was added because it was erroneously omitted.
- For erroneous entry, “after final administration” described in Protocol 6.2 Pharmacodynamics was changed to “after administration on Day 5.”
- For erroneous entry, “Analysis of covariance using baseline weight as covariate will be performed on the change (absolute change and percent change)” described in

Protocol 7.4.1 Body Weight was changed to “Analysis of covariance using baseline weight as covariate will be performed on the change.”

- Because the evaluation of multiple sections all together is difficult, it was decided not to summarize for other edema described in Protocol 7.4.2.1.
- Because of the low number of applicable subjects, hepatomegaly described in Protocol 7.4.2.2. was eliminated from the list for analysis of covariance

15 References

¹ Package insert for Samsca tablet (tolvaptan tablet) 7.5 mg, 15 mg, 30 mg

